#### 4.2.5 Sensitivity Analyses

As a sensitivity analysis for the MDS-UPDRS Parts II + III, the MMRM will be repeated as described in [Section 4.2.3](#) using the FAS.

Any efficacy endpoints that reach statistical significance may also be further explored on a post hoc basis using sensitivity analysis in which the Hypothetical Scenario is applied to Intercurrent Events, using the assumptions of Missing at Random (MAR) and Missing Not at Random (MNAR), respectively, to perform Multiple Imputation (MI) to impute data after the first occurrence of PD medication use. For MI using MNAR, copy-reference (placebo) will be used.

#### 4.2.6 Pharmacokinetic Analysis

Pharmacokinetic samples will be drawn predose at baseline and postdose at Weeks 4, 8, and 12.

IKT-148009 concentration will be listed and descriptively analyzed by treatment group for the PK analysis set. Descriptive statistics include N, mean, geometric mean, SD, SEM, median, %CV, minimum and maximum. Concentrations that are below the limit of quantitation (BLQ) will be treated as zero for the determination of summary statistics and will be treated as missing for the calculation of the geometric means.

Mean (+/- SD) of plasma IKT-148009 concentrations will be plotted by treatment at each time point.

### 4.3 SAFETY ANALYSIS

All safety assessments will be performed on the Safety Analysis. Safety data presented by treatment group will be summarized on an ‘as treated’ basis. Safety variables include treatment-emergent adverse events (TEAEs), clinical laboratory parameters, vital signs, 12-lead ECG results, ophthalmic exams, suicidality, and extent of exposure. Study Day 1 for all safety analyses is defined as the date of the first dose of study drug. Safety and tolerability endpoints will be assessed at Week 12. Tolerability will be assessed by

comparing percentages of premature drug and study discontinuations in the treatment.

#### 4.3.1 Extent of Exposure

Time on treatment will be defined as the *date of last dose – date of first dose + 1*. Total dose will be defined as the *time on treatment × actual dose level*. Temporary interruptions in dosing or missed doses will not be considered. Time on treatment and total dose will be summarized by dose group for the safety analysis set.

#### 4.3.2 Adverse Events

Treatment emergent adverse events (TEAEs) are defined as those that start or worsen after the first dose of study intervention until the Safety follow-up visit is completed. Safety assessments will include TEAEs tabulated by treatment group; descriptive statistics for continuous variables and frequency counts for discrete variables. No inferential statistical analysis is planned for safety data.

TEAEs will be summarized by treatment group. The incidence of TEAEs will be reported as the number (percent) of participants with TEAEs within system organ class (SOC) and preferred term (PT). Participants will be counted only once within a SOC and PT, even if the participant experienced more than one TEAE within a specific SOC and PT.

TEAEs will also be summarized by dose group, SOC and PT for the following:

1. By maximum severity
2. By relationship to study drug
3. By seriousness
4. Related TEAEs of moderate or severe intensity
5. Leading to withdrawal of study drug
6. Serious Adverse Events (SAE)
7. Suicidality as measured by the C-SSRSSafety and tolerability endpoints will be summarized for the end of the week-12 placebo-controlled study.

Supportive listings will be provided for each summary table. The AE listing will include day of onset and end day.

#### 4.3.3 Deaths

All deaths will be reported as AEs. The cause of death will be defined as the Preferred Term for the AE with an outcome of “fatal”, and the date of death will be defined as the end date of that AE. A participant data listing of all deaths will be provided, including which AE led to death.

#### 4.3.4 Clinical Laboratory Data

Clinical laboratory tests (hematology and clinical chemistry) and their central reference ranges are listed in [Table 4-4](#) and Table 4-5.

**Table 4-4 Hematology tests and reference ranges**

Laboratory test	Lower limit of normal	Upper limit of normal	Units
WBC	Over 16 yr: 4.1	12.3	$\times 10^3/\mu\text{L}$
Hemoglobin	Female 12-65 yr: 11.6	Female 12-65 yr: 16.2	$\text{g/dL}$
	Female 66-110 yr: 11.0	Female 66-110 yr: 16.1	
	Male 18-65 yr: 13.0	Male 18-65 yr: 17.5	
	Male 66-110 yr: 13.0	Male 66-110 yr: 17.7	
Hematocrit	Female 12-65 yr: 35.0	Female 12-65 yr: 47.0	$\%$
	Female 66-110 yr: 33.0	Female 66-110 yr: 46.0	
	Male 18-65 yr: 40.0	Male 18-65 yr: 52.0	
	Male 66-110 yr: 37.0	Male 66-110 yr: 50.0	
RBC count	Female 12-65 yr: 3.8	Female 12-65 yr: 5.5	$\times 10^6/\mu\text{L}$
	Female 66-110 yr: 3.8	Female 66-110 yr: 5.40	
	Male 18-65 yr: 4.1	Male 18-65 yr: 5.9	
	Male 66-110 yr: 4.0	Male 66-110 yr: 5.8	
MCV	Female: 79	98	$\text{fL}$
	Male: 79	97	
MCH	26	34	$\text{Pg/cell}$
MCHC	31	37	$\text{g/dL}$
RDW	11.6	14.8	$\%$
Platelet count	140	450	$\times 10^3/\mu\text{L}$
Neutrophils	40.9	77.0	$\%$
Lymphocytes	15.5	16.6	$\%$
Monocytes	3.1	12.5	$\%$
Eosinophils	0.0	6.0	$\%$
Basophils	0.0	2.4	$\%$
Blasts	0	0	$\%$
Promyelocytes	0	0	$\%$
Myelocytes	0	0	$\%$
Metamyelocytes	0	0	$\%$
Bands	0.0	5.0	$\%$
Prolymphocytes	0	0	$\%$
Atypical lymphocytes	0	3	$\%$
Neutrophils Absolute	2.03	8.36	$\times 10^3/\mu\text{L}$
Lymphocytes Absolute	1.02	3.36	$\times 10^3/\mu\text{L}$
Monocytes Absolute	0.18	0.90	$\times 10^3/\mu\text{L}$
Eosinophils Absolute	0.00	0.56	$\times 10^3/\mu\text{L}$
Basophils Absolute	0.00	0.17	$\times 10^3/\mu\text{L}$
Blasts Absolute	0.00	0.00	$\times 10^3/\mu\text{L}$
Promyelocytes Abs	0.00	0.00	$\times 10^3/\mu\text{L}$
Myelocytes Absolute	0.00	0.00	$\times 10^3/\mu\text{L}$
Metamyelocytes Absolute	0.00	0.00	$\times 10^3/\mu\text{L}$
Bands Absolute	0.00	0.50	$\times 10^3/\mu\text{L}$
Prolymphocytes Absolute	0.00	0.00	$\times 10^3/\mu\text{L}$
Atypical lymphocytes Absolute	0.00	0.30	$\times 10^3/\mu\text{L}$
Nucleated RBC	0	0	$/100\text{WBC}$
Plasma cells Absolute	0.00	0.00	$\times 10^3/\mu\text{L}$
Plasma cells	0	0	$\%$
Reticulocytes	0.3	2.8	$\%$
Reticulocytes Absolute	13.5	123.0	$\times 10^3/\mu\text{L}$

MCV = mean corpuscular volume; MCH= mean corpuscular hemoglobin; RBC = red blood cell; RDW = red cell distribution width; WBC = white blood cell.

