### **3.4.3 Clinical Laboratory Variables**

Laboratory safety assessments will be performed in a central laboratory at each Visit. The hematology, clinical chemistry, urinalysis, and other parameters are outlined in Appendix 2 of the protocol. Laboratory data are to be reported in SI units, except for the blood eosinophils counts which will be reported in conventional units.

For values recorded with a leading greater than or less than ('>', '<') symbol, the reported numeric value will be used for analysis and the value with the symbol will be included in the listings, unless otherwise specified. For example, a value of <0.01 will be analyzed as 0.01 and listed as <0.01.

Absolute values will be compared to the relevant reference range and classified as LNH (low (below normal limit), normal (within normal limits) or high (above normal limit)). The central laboratory ranges will be used for laboratory variables. All absolute values falling outside the reference ranges will be flagged as L (low) or H (high).

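### SAP Table 4-4 gives percentage lymphocytes an upper limit of 16.6%, which is inconsistent with the other rows of the same table and makes the flags unreliable if the table is programmed

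*SAP*

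**What the plan says.** SAP Table 4-4 gives the percentage-lymphocyte row as "Lymphocytes 15.5 16.6". The other differential rows in the table are "Neutrophils 40.9 77.0", "Monocytes 3.1 12.5", "Eosinophils 0.0 6.0", "Basophils 0.0 2.4" and "Atypical lymphocytes 0 3", with bands at 0.0 to 5.0, all in percent. The remaining immature or abnormal cell types have limits of zero. The table also gives a white cell count range of 4.1 to 12.3 and an absolute lymphocyte range of 1.02 to 3.36, both in thousands per microlitre.

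SAP section 4.3.4 introduces the tables with these words: "Clinical laboratory tests (hematology and clinical chemistry) and their central reference ranges are listed in" Tables 4-4 and 4-5. SAP section 3.4.3 states the classification rule: "Absolute values will be compared to the relevant reference range and classified as LNH", meaning Low, Normal or High. It adds that the central laboratory's ranges apply and that results outside them are flagged. Section 4.3.4 then requires a shift table from baseline for each laboratory parameter. It defines a treatment-emergent abnormal value as one that is new after dosing or that worsens an abnormality already present.

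Neither document gives any other range for percentage lymphocytes.

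**The concern.** Differential percentages add up to 100, so the range for one cell type has to be compatible with the ranges for the others. Neutrophils are allowed a span of 36.1 points (77.0 − 40.9) and lymphocytes a span of 1.1 points (16.6 − 15.5). When neutrophils sit low in their normal range, another cell type has to make up the difference, and the remaining rows leave too little room for anything but lymphocytes to do so.

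The stake is one parameter in the descriptive safety evaluation. If the printed limit is the one programmed, a participant could be Normal on absolute lymphocytes and High on percentage lymphocytes from the same sample. A rise from a value already above 16.6% would appear as High to High. A fall from, say, 28% to 16% would appear as a return to normal. Small fluctuations across a 1.1-point band would register as shifts.

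**Working it through.** The range is a listed input and not a derived figure, so there is no calculation in the plan to reproduce. The check is whether the row is consistent with the rest of Table 4-4, and every input comes from that table.

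**Step 1: differential closure, without bands or atypical lymphocytes.**
Lymphocytes % = 100 − neutrophils − monocytes − eosinophils − basophils.
- Upper limits of the last three: 12.5 + 6.0 + 2.4 = 20.9.
- Lymphocytes are at or below 16.6 only if neutrophils are at least 100 − 16.6 − 20.9 = 62.5.
- Share of the width of the normal neutrophil range below that threshold: (62.5 − 40.9) / (77.0 − 40.9) = 21.6 / 36.1 = 60%.

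**Step 2: the same, with bands and atypical lymphocytes at their upper limits.** This case is the most lenient to the printed range, because it leaves the least room for lymphocytes.
- Additional cells: 5.0 + 3 = 8.0.
- Threshold: 62.5 − 8.0 = 54.5.
- Share of the width: (54.5 − 40.9) / 36.1 = 13.6 / 36.1 = 38%.
- With neutrophils at their lower limit, lymphocytes are 100 − 40.9 − 20.9 − 8.0 = 30.2%, well above 16.6%.

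Lower values for the other cell types, still within their ranges, only push lymphocytes higher. So 54.5% is a firm threshold for anyone whose other rows are all normal.

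**Step 3: absolute counts.**
Lymphocytes % = 100 × absolute lymphocytes / white cell count.
- The lowest normal absolute count, 1.02, exceeds 16.6% whenever the white cell count is below 1.02 / 0.166 = 6.1. Below that count, every normal absolute value is above the printed upper limit.
- At the highest normal white cell count, 12.3, an absolute count of 0.166 × 12.3 = 2.04 corresponds to 16.6%. Any absolute count from above 2.04 up to the normal limit of 3.36 therefore exceeds 16.6% at every normal white cell count.

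**Step 4: the lower limit.** The same checks show no conflict with 15.5%. The inconsistency lies in the upper limit.

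**The case against.** The strongest objection is that the printed table may never reach the analysis. SAP section 3.4.3 already says the central laboratory's ranges govern, and nowhere does the SAP say that flags will be programmed from Tables 4-4 and 4-5. The tables would make a poor programming source. Creatinine clearance and FSH carry no limits in the text available, and LH has limits only for men aged 18 to 49 although the trial enrols men and women aged 30 to 80. Many rows are in conventional units where the SAP calls for SI units. If the ranges delivered with the data are correct and are used, this is a slip in a listing with no effect on results. That stands, and it is why the consequence has to be conditional. It does not clear the row, because section 4.3.4 presents these tables as the central ranges and no text says which source prevails if they differ.

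A second objection concerns size. A reader might infer from step 1 that every participant with neutrophils between 40.9% and 62.5% must be flagged High. The table does not support that, because it allows bands and atypical lymphocytes; with those at their limits the threshold is 54.5%, and even then all other rows must be in range. A reader might also infer that 24.9% (1.02 / 4.1) and 27.3% (3.36 / 12.3) are the percentages the absolute limits imply. Pairing low with low and high with high is arbitrary. The same limits allow anything from 8.3% (1.02 / 12.3) to 82% (3.36 / 4.1), and that interval contains 15.5 to 16.6. The absolute rows show that many normal counts would be flagged. They do not by themselves exclude the printed range.

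A third objection concerns consequence. A reader might infer that real rises would be hidden. The shift table would lose them, but section 4.3.4 also summarises observed values and changes at each time point and lists every result. Absolute lymphocytes keep their own range and shift table. Worsening of an existing abnormality still counts as treatment-emergent. Laboratory adverse events depend on the investigator's judgement of clinical significance and not on the flag.

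**Conclusion.** The upper limit of 16.6% is inconsistent with the rest of Table 4-4. With all other cell types in range, at least 38% of the width of the normal neutrophil range forces a High lymphocyte percentage, and 60% does so if bands and atypical lymphocytes are absent. Every normal absolute count is High when the white cell count is normal but below about 6.1.

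If Table 4-4 supplies the flags, the percentage-lymphocyte shift table and the treatment-emergent status for that parameter are unreliable. If correct laboratory-delivered ranges are used, the error stays in the SAP table.

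It is tempting to conclude that most participants would be High at baseline. The documents do not support a statement about participants: a share of the width of a reference range is not a share of people, and no distribution is given. Assuming a uniform, independent spread over the table's own normal ranges gives about 84% High, 13% Low and 3% Normal, but that rests entirely on the assumption.

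Absolute-lymphocyte classification, change-from-baseline summaries, listings, adverse event counts, tolerability and efficacy are not affected. The text was extracted from PDF, so a misread digit cannot be fully excluded. This is a minor correction.

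**What to change.** - Check the percentage-lymphocyte cell against the original page of SAP Table 4-4.
- If 16.6 is confirmed there, replace the row with the central laboratory's certified range. The documents do not contain the correct upper limit, so no figure is proposed here.
- Add one sentence to SAP section 3.4.3 or 4.3.4 stating that Low/Normal/High flags are taken from the ranges delivered with the central-laboratory results, and that Tables 4-4 and 4-5 are for reference only.

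The cost is one table cell and one sentence. No analysis, sample size or data collection changes.

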**Table 4-5 Clinical chemistry tests and reference ranges**

Laboratory test	Lower limit of normal	Upper limit of normal	Units
Sodium	135	147	mEq/L
Potassium	3.3	5.1	mEq/L
Bicarbonate	19	29	mEq/L
BUN/Urea	18-60 yr: 6 61-110 yr: 8	20 23	mg/dL
Creatinine	Female: 0.51 Male: 0.67	0.95 1.17	mg/dL
Creatinine Clearance			
Glucose (non-fasting)	16-59 yr: 74 60-90 yr: 82 91-109 yr: 75	106 115 121	mg/dL
Lipase	Over 16yr: 13	60	U/L
Calcium	12-65 yr: 8.4 66-90 yr: 8.8 91-109 yr: 8.2	10.3 10.2 9.6	mg/dL
Phosphorus	2.5	4.5	mg/dL
Magnesium	1.3	2.1	mEq/L
Protein Total	6.0	8.0	g/dL
Albumin	3.5	5.2	g/dL
Bilirubin Total	≤ 1.2		mg/dL
Bilirubin Direct	≤ 0.3		mg/dL
ALT	Female: ≤33 Male: ≤41		U/L
AST	Female: ≤31 Male: ≤37		U/L
GGT	Female: 5 Male: 8	36 61	U/L
Alkaline phosphatase	Female: 35 Male: 40	104 129	U/L
LDH	≤250		U/L
CK	Female: 26 Male: 39	192 308	U/L
Uric acid	Female: 2.4 Male: 3.4	5.7 7.0	mg/dL
Amylase total	28	100	U/L
eGFR/1.73m  CKD-EPI		≥60	mL/min
LIPID PANEL			
Cholesterol	<200		mg/dL
Triglycerides	<150		mg/dL
URINALYSIS			
Urine dipstick appearance	CLEAR		
Urine dipstick bilirubin	NEGATIVE		
Urine dipstick blood	NEGATIVE		
Urine dipstick color	YELLOW		
Urine dipstick glucose	NEGATIVE		
Urine dipstick ketones	NEGATIVE		
Urine dipstick leukocyte esterase	NEGATIVE		

Urine dipstick nitrite	NEGATIVE		
Urine dipstick pH	5.0	8.0	
Urine dipstick protein	NEGATIVE		
Urine dipstick specific gravity	1.001	1.035	
Urine dipstick urobilinogen	NORMAL/TRACE		
Urine dipstick microscopy	NORMAL		
Urinalysis RBC	Male: 0	5	HPF
	Female: 0	8	
Urinalysis WBC	Male: 0	3	HPF
	Female: 0	12	
COAGULATION			
Prothrombin time	Over 1 yr: 10.0	14.3	sec
INR	0.8	1.2	
ENDOCRINOLOGY			
B-hCG	NEGATIVE		
FSH			mIU/mL
LH	Male 18-49yr: 1.5	9.3	mIU/mL
Testosterone Total	Male 18-49yr: 123.06	813.86	ng/dL
	Male ≥50yr: 86.98	780.10	
THYROID PANEL			
TSH	0.55	4.78	uIU/mL
TESTED at QD Nichols Institute			
Inhibin B	Male: 47	308	pg/mL
ALT = alanine aminotransferase; AST = aspartate aminotransferase; BUN = blood urea nitrogen; CK = creatine kinase; CKD-EPI = chronic kidney disease epidemiology collaboration; eGFR = estimated glomerular filtration rate; GGT = gamma glutamyl transferase; LDH = lactate dehydrogenase; RBC = red blood cells.			

A treatment-emergent abnormal value is an abnormality that was not present before dosing, but was present after dosing, or one that represents an exacerbation of a pre-existing abnormal value based on baseline.

Laboratory values that are non-missing and reported as 'below the detectable limit' of an assay will be replaced by the detectable limit in the summary tables. Laboratory results will be summarized using International System (SI) units.

Baseline, observed value for each time point, and changes in hematology and clinical chemistry variables for each time point will be summarized using descriptive statistics for the Safety analysis set by treatment group.

Each laboratory parameter will have shift tables presented that compare the baseline LNH classification to the LNH classification at each post-baseline visit and at the end of treatment.

All laboratory values will be listed by participant for the safety analysis set.

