6.2. Exclusion Criteria

Participants are excluded from the study if any of the following criteria apply:

Medical Conditions

1. Diagnosis/suspicion of secondary or atypical parkinsonism
2. Previous procedure or surgery for PD, or anticipation of these during the study
3. High likelihood of needing anti-parkinsonian treatment over the study period, in the opinion of the investigator
4. Clinically significant orthostatic hypotension
5. Clinically significant hallucinations requiring antipsychotic use in the 12 months prior to Screening
6. Clinically significant medical, surgical, psychiatric, or laboratory abnormalities in the judgement of the treating investigator or the EAC

Prior/Concomitant Therapy

1. Past treatment with levodopa, dopaminergic agonists, monoamine oxidase-B inhibitors, supplements containing levodopa (i.e. *Mucuna pruriens*) or A2A antagonists for more than 28 days, or treatment with any of these medications or supplements within 28 days prior to screening
2. Past treatment with irreversible monoamine oxidase-B inhibitors (e.g., selegiline) for more than 28 days; must be discontinued for at least 90 days before screening
3. Currently receiving moderate or strong Cytochrome P450 (CYP) 3A4/5 inducers or CYP3A4/5 inhibitors (except for topical administration)

4. Currently receiving any antipsychotic, metoclopramide, reserpine, or amphetamine.

Prior/Concurrent Clinical Study Experience

1. Current participation in another investigational clinical trial and/or receipt of any investigational medication within 90 days prior to screening
2. Previous randomization into this or another IkT-148009 study

Diagnostic Assessments

1. Active suicidal ideation within one year prior to screening visit, as determined by the Columbia Suicide Rating Scale (answer of “yes” on question 4 or 5)
2. Current diagnosis or history of substance abuse (excluding nicotine or caffeine) by Diagnostic and Statistical Manual of Mental Disorders (DSM)-5 criteria
3. Medical or recreational use of marijuana in the 3 months prior to the screening visit
4. Any social or behavioral reason that would preclude completion of the study, in the judgement of the investigator
5. Any skin condition that would interfere with obtaining adequate samples

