6. Evidence of advanced, age-related macular degeneration (neovascular or geographic atrophy) or intermediate macular degeneration as defined by Beckman classification (Large drusen > 125 um and/or any AMD pigmentary abnormalities). Evidence of retina/choroid neovascularization from any cause. Evidence of central serous retinopathy.
7. Abnormal amylase and/or lipase at screening (may be repeated during screening period)
8. Alanine aminotransferase (ALT) or aspartate aminotransferase (AST) levels greater than 2.5 times the upper limit of normal (ULN)
9. Significant renal impairment as determined by the following criteria:
 - Creatinine clearance (CrCL) less than or equal to 60 mL/min for subjects < 65 years of age
 - Creatinine clearance (CrCL) less than 55 mL/min or the presence of other evidence of chronic kidney disease such as proteinuria for subjects ≥ 65 years of age
10. Currently lactating, pregnant or planning on becoming pregnant during the study

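### The SAP's only categorical laboratory table is a Low/Normal/High shift, so no planned table counts participants per arm by how far ALT, AST or bilirubin rises

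*SAP*

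**What the plan says.** **Classification.** SAP 3.4.3 compares each value with the central laboratory range and sorts it into three classes: low, "normal (within normal limits) or high (above normal limit"). No grades or multiples of ULN are used.

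**Tables.** SAP 4.3.4 then states: "Each laboratory parameter will have shift tables presented that compare the baseline LNH classification to the LNH classification at each post-baseline visit", and also at end of treatment. For the same variables, "changes in hematology and clinical chemistry variables for each time point will be summarized using descriptive statistics", by treatment group in the Safety set. SAP 2.1 includes the minimum and maximum among those statistics. All laboratory values are listed by participant.

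**Treatment-emergent abnormality.** SAP 4.3.4 covers a new abnormality "or one that represents an exacerbation of a pre-existing abnormal value based on baseline". It does not say how large an exacerbation must be, and ties no count or table to the definition.

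**Entry.** Protocol 6.2, diagnostic exclusion 8, removes "Alanine aminotransferase (ALT) or aspartate aminotransferase (AST) levels greater than 2.5 times the upper limit of normal (ULN"). Medical exclusion 6 adds a discretionary bar without a number: "Clinically significant medical, surgical, psychiatric, or laboratory abnormalities in the judgement of the treating investigator or the EAC".

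**Limits.** SAP Table 4-5 gives ALT as "Female: ≤33 Male: ≤41" and AST as "Female: ≤31 Male: ≤37", in U/L.

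**Adverse events.** Protocol 9.2.4, 9.3.1 and 10.3.1 make a laboratory change an adverse event when the investigator judges it clinically significant, including worsening of a baseline abnormality. SAP 4.3.2 tabulates treatment-emergent events by dose group.

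**The concern.** Safety and tolerability are the primary objective (SAP 1.1.1). They are assessed descriptively, without hypothesis tests, and laboratory change is a named component (Protocol 5.4.2, SAP 3.4). The descriptive tables are therefore the main evidence on whether enzyme elevations increase across three doses.

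A three-class shift table answers a narrow question: did the participant cross the limit? It does not say by how much. It also records no shift for a participant who starts above the limit and worsens, and the entry criteria allow such participants. The SAP recognises worsening from an abnormal baseline as treatment-emergent, then never counts it. At stake is whether a reader of the by-arm tables can see how many participants in each arm had a marked elevation, rather than any elevation.

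**Working it through.** The plan gives no figure for this point, so there is none to reproduce. The check puts values through the SAP's own rule: High if above ULN. On-drug values are illustrative, because the documents give none.

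**Step 1. What may enter.** Ceiling = 2.5 x ULN (Protocol 6.2 with SAP Table 4-5).

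| Test | ULN (U/L) | 2.5 x ULN (U/L) | Class |
|---|---|---|---|
| ALT, female | 33 | 82.5 | High |
| ALT, male | 41 | 102.5 | High |
| AST, female | 31 | 77.5 | High |
| AST, male | 37 | 92.5 | High |

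Anything above 1 x and up to 2.5 x ULN passes exclusion 8 and is classed High, unless exclusion 6 is invoked.

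**Step 2. What the shift table shows (male ALT, ULN 41).**

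| Baseline | On drug | Shift cell |
|---|---|---|
| 40 U/L | 42 U/L | Normal-to-High |
| 100 U/L (100/41 = 2.4 x) | 400 U/L (400/41 = 9.8 x) | High-to-High |
| 102.5 U/L (2.5 x) | 123, 205, 328 or 820 U/L (3, 5, 8 or 20 x) | High-to-High each time |
| 36.9 U/L (0.9 x) | 45.1 U/L (1.1 x) | Normal-to-High |
| 36.9 U/L (0.9 x) | 820 U/L (20 x) | Normal-to-High |

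The first two rows show a 2 U/L change registering as a shift and a 300 U/L change not doing so. The last two show that the limitation does not depend on an elevated baseline.

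**Step 3. What the continuous summaries add.** Take an arm of 30 (SAP 1.3.3) in which one man goes from 2.5 to 8 x ULN.

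- Maximum change = (8 − 2.5) x 41 = +225.5 U/L, which is visible.
- Effect on the mean change = 225.5/30 = about 7.5 U/L, which is small.

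If five men had that same rise, the maximum change would still print as +225.5 U/L, and the mean would move by 5 x 225.5/30 = about 37.6 U/L. Read with the SD and median, this would suggest more than one large rise. It would not give the number.

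**Step 4. Time points.** The laboratory tables are by visit or end of treatment. One participant may be High at several visits, so visit counts cannot be added to give the number ever affected. No table takes each participant's worst value. Protocol 9.2.4 requires repeat testing of clinically significant results, so the worst value may fall outside a scheduled visit.

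**The case against.** The best reply is that the rises are not hidden. By-arm summaries of observed values and changes carry the maximum, so the 100 to 400 U/L case would contribute a maximum of 400 and a change of +300 at that visit unless another participant exceeded it. All values are listed, and Protocol 5.4.5 adds a separate listing of abnormal results. Clinically significant worsening from an abnormal baseline becomes an adverse event and reaches the incidence tables by severity and relationship. The DSMB reviews safety data regularly. The SAP also does what Protocol 5.4.5 asks in providing shift tables, no estimate is biased, and all data are kept.

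This stands as far as visibility goes. A reader might infer that marked elevations would be found only by reading listings. The documents do not support that, because maxima and adverse event tables are also by arm.

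It does not supply the count. A maximum shows that at least one extreme value exists. The adverse event route depends on each investigator's view of clinical significance, and the recorded intensity does not give the size of the rise: Protocol 10.3.3 allows an asymptomatic laboratory observation to be graded mild.

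Two other inferences should be resisted. A reader might suppose that the affected participants have the least hepatic reserve; nothing in the documents links ALT or AST between 1 and 2.5 x ULN to hepatic reserve, and exclusion 6 may remove some of these people. A reader might also extend the elevated-entry argument to lipase and amylase; diagnostic exclusion 7 bars abnormal screening values for both, so it largely does not apply.

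**Conclusion.** The point holds as a gap in tabulation. The only categorical laboratory table cannot distinguish a marginal from a marked elevation, records worsening from a High baseline as no shift, and leaves the SAP's own definition of exacerbation without a threshold or a count. No planned table gives the number of participants per arm by size of elevation.

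The size of the gap is structural: every multiple tested, from 3 to 20 x ULN, falls in the same cell as 1.1 x ULN when the baseline class is the same. Its practical frequency is unknown, since the documents give neither the share entering above ULN nor any on-drug enzyme values. They indicate no hepatic signal, and none is assumed here.

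The conclusion rests on reading the eligibility limit as allowing High baseline values, and on the SAP text being the full list of planned laboratory tables. It is a worthwhile improvement to a trial whose primary objective is descriptive safety. It does not invalidate the planned analyses.

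**What to change.** Keep the shift tables and make two changes.

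1. **Add one by-arm Safety set table of worst post-baseline values.** For ALT, AST and total bilirubin, take each participant's highest post-baseline value, including unscheduled samples, and count participants in pre-specified ULN multiples, for example ≤1, >1 to 2.5, >2.5 to 5, >5 to 8 and >8. For ALT and AST, add fold-change from baseline in those above ULN at baseline. Add a count of participants with concurrent ALT or AST and bilirubin elevations, at cut-points fixed in advance.

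2. **Complete the definition of exacerbation.** For High baselines, state a fold-over-baseline reporting threshold, then tabulate treatment-emergent abnormal values by arm. Moving up one band would be a poor rule: 1.1 to 2.4 x ULN would not count, while 2.49 to 2.51 x ULN would. Worsening of a Low baseline needs its own rule, because multiples of ULN cannot describe it.

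Apart from 2.5 x ULN, the bands shown are suggestions and do not come from the documents. They are reporting cut-points only and carry no implication for participant management. The sponsor should fix them before unblinding.

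The cost is one extra table, one definition with its tabulation, and the need to agree cut-points. No new data are required.
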